Study Protocol and Statistical Analysis Plan

Official title: The effect of Er,Cr:YSGG laser-assisted topical anesthetic on oral mucosal anesthesia

NCT number: NCT07169032

Document date: 12/25/2023

This study is a randomized controlled clinical trial with a single-blind design. The protocol has been approved by the Medical Ethics Review Committee of Jinan University (Approval No.: JNUKY-2023-0149). All participants will provide written informed consent before the study begins.

1. Study Participants

The study will be conducted in an outpatient setting, with a total of 20 participants (10 males and 10 females). Participants will be recruited through online advertisements and from among outpatient clinic visitors. All participants will receive free oral health examinations and related treatments as compensation.

1.1 Inclusion Criteria

- Aged 20–45 years;
- Able to understand and follow verbal and written instructions.

1.2 Exclusion Criteria

- Severe dental anxiety;
- Allergy to local anesthetics;
- Presence of oral mucosal lesions;
- History of cardiovascular disease;
- History of diabetes;
- Pregnant or lactating women;
- History of severe psychiatric disorders;
- Hearing or speech impairments.

2. Group Allocation

This is a single-blind randomized controlled trial. After providing informed consent, participants will be stratified by gender. Three sites in the mandibular anterior

vestibular groove will be selected and randomly assigned to one of the following three interventions:

- Experimental group: Irradiation with Er,Cr:YSGG water laser (wavelength 2780 nm, power 1.0 W) for 1 minute, followed by application of 2% lidocaine gel;
- Control group: Irradiation with placebo laser (0.1 W) for 1 minute, followed by application of 2% lidocaine gel;
- Blank group: Irradiation with placebo laser (0.1 W) for 1 minute, followed by application of petroleum jelly.

All procedures will be performed by the same operator and assistant. Participants will be blinded to group assignment.

3. Materials and Equipment

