3.1 Experimental Equipment

3.1.1 Water Laser Device

Device: Er,Cr:YSGG Waterlase (Model MDX300), manufacturer: BOOLASE (USA), registration number: National Medical Device Approval 20153241177. The laser wavelength is 2780 nm and is suitable for various dental procedures. Two modes are predefined:

- Mode 1a (active laser): Power 1.0 W, water 15%, air 35%, frequency 30 Hz, H mode (soft tissue mode);
- Mode 1b (placebo laser): Power 0.1 W, other parameters same as Mode 1a.

All personnel must wear laser protective glasses during operation. The handpiece must be moved continuously to avoid localized heat accumulation.

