3.1.3 Visual Analog Scale (VAS)

A 10 cm linear VAS will be used to assess pain intensity, ranging from "no pain" (0) to "worst pain imaginable" (10). Participants will slide the indicator to reflect their subjective pain level, and the operator will record the corresponding value.

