3.2 Experimental Drugs and Materials

- Topical anesthetic: 2% lidocaine gel (Gandermal, Registration No.: H20150426);
- Placebo: Petroleum jelly;
- Other materials: 27G injection needle (Fukada), periodontal probe (Hu-Friedy), mouth prop (Ivoclar), dental mirror, sterile cotton swabs, timer, etc.

4. Outcome Measures

Primary outcome measures include:

- Penetration depth and VAS score at the moment of "sensation of foreign body";
- Penetration depth and VAS score at the moment of "pain";
- Heart rate at each needle insertion and the increase in heart rate (heart rate at pain moment – baseline heart rate).
- Penetration depth is calculated based on the exposed length of the needle (penetration depth = 30 mm – length outside the mucosa).

5. Study Procedure

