5.1 Preparation Phase

- Participants will rest for 30 minutes after signing consent to stabilize vital signs;

- Baseline heart rate will be recorded. Laser protective glasses and ECG monitoring devices will be worn;
- The operator will preset the laser device parameters.

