5.2 Experimental Procedure

- Three sites in the maxillary anterior vestibular groove with intervals >20 mm will be selected;
- Interventions will be applied in random order (laser irradiation and subsequent drug application);
- Penetration tests will be performed at 10, 20, 30, 40, and 50 minutes after treatment. Penetration depth, VAS score, and heart rate will be recorded at the moments of "sensation" and "pain";
- Adverse reactions (redness, pain, bruising, etc.) will be assessed immediately after the procedure and at 24-hour follow-up.

6. Statistical Analysis

- Data will be analyzed using SPSS 27.0. Normally distributed continuous variables will be expressed as mean \pm standard deviation ($\bar{x} \pm s$);
- Repeated measures ANOVA will be used to compare differences across time points and groups. If the sphericity assumption is violated, multivariate tests (Roy's Max Root) will be applied;
- Pairwise comparisons will be performed using Bonferroni correction with significance level $\alpha = 0.05$;
- A p-value < 0.05 will be considered statistically significant

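### Only participants are blinded; nothing masks the person who advances the needle and reads penetration depth, so a primary outcome is open to observer bias of unknown size and direction

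*Combined protocol and SAP*

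**What the plan says.** The opening design statement reads: "This study is a randomized controlled clinical trial with a single-blind design". Section 2 repeats the single-blind label and says who is blinded: "All procedures will be performed by the same operator and assistant. Participants will be blinded to group assignment". No other role is described as blinded.

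On the laser, section 3.1.1 says "Two modes are predefined", the second being "Mode 1b (placebo laser): Power 0.1 W, other parameters same as Mode 1a". Section 5.1 adds: "The operator will preset the laser device parameters". Section 5.2 says: "Interventions will be applied in random order (laser irradiation and subsequent drug application".

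On measurement, section 4 lists depth and VAS at the foreign-body sensation and at pain, together with heart rate, as primary outcomes. It explains: "Penetration depth is calculated based on the exposed length of the needle", that is, 30 mm minus the length outside the mucosa. For VAS, section 3.1.3 says: "Participants will slide the indicator to reflect their subjective pain level, and the operator will record the corresponding value". Section 5.2 sets penetration tests at five times from 10 to 50 minutes.

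**The concern.** Depth is not read off an instrument. Someone pushes the needle forward, stops when the participant signals, and judges how much needle is still exposed. If that person knows which site had the active laser, each of these steps can shift slightly and consistently with the allocation.

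The comparison most at stake is Experimental versus Control. Both receive the same 2% lidocaine gel and differ only in laser power (1.0 W against 0.1 W), so this contrast isolates the laser's contribution, which is the question in the trial's title. For the same reason it is the contrast for which masking the tester is most practicable, since the applied material does not give the allocation away.

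The other primary outcomes are less exposed. The participant sets the VAS indicator, and heart rate comes from a monitor.

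**Working it through.** The plan states no figure that could be reproduced: it gives no power, SD or expected difference. The check is therefore first a reading of the text, then an illustration on assumed values.

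**What the text settles**

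| Question | Where | Answer |
|---|---|---|
| Who is blinded? | Opening statement; section 2 | Participants only |
| Who may do the penetration tests? | Section 2 | The operator or the assistant |
| Which of the two tests and reads depth? | Sections 2, 4, 5.2 | Not stated |
| Is the tester unaware of the allocation? | All sections | Not stated |
| Who presets the laser and records VAS? | Sections 5.1, 3.1.3 | The operator |
| Is there a standard advance, stopping procedure or second reading? | Sections 4, 5.2 | None described |
| What sets the moment of reading? | Sections 4, 5.2 | The participant's sensation or pain |

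The participant's perception fixes when the depth should be read. What stays with staff is needle speed, promptness in stopping and the reading.

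**How many tests are involved, if every site is tested at every time**

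- All groups: 20 × 3 × 5 = 300.
- Experimental and Control: 20 × 2 × 5 = 200.
- First tests at a site (10 minutes): 20 × 3 = 60. Later tests at the same site: 20 × 3 × 4 = 240.

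A handling difference that is consistent between sites does not average out over these tests.

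**Illustration: false-positive rate under an assumed bias**

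From the documents: n = 20 and α = 0.05. Assumed: no true difference, a constant bias b, a two-sided paired t-test in place of the planned repeated measures ANOVA, and Bonferroni over three group pairs (0.05/3 = 0.0167).

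Rate = 1 − F(t*; 19, δ) + F(−t*; 19, δ), where F is the noncentral t distribution function with 19 degrees of freedom and δ = b√20. The critical value t* is 2.093 at 0.05 and 2.625 at 0.0167.

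| Bias b, in SD of the paired difference | δ | Rate at 0.0167 | Rate at 0.05 |
|---|---|---|---|
| 0.05 | 0.224 | 1.9% | 5.5% |
| 0.10 | 0.447 | 2.6% | 7.1% |
| 0.25 | 1.118 | 8.8% | 18.6% |
| 0.50 | 2.236 | 37.3% | 56.5% |

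At 0.0167 the rate stays at or below 5% until b is about 0.18. At 0.05 it reaches 10% at b of about 0.15.

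**How far the result depends on the scale of the bias**

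Suppose the bias is instead given in SDs of a single site reading within a participant.

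- One time point: the paired-difference SD is larger by √2, so b is divided by √2.
- Mean of five independent readings, with the same bias at each time: b is multiplied by √(5/2) = 1.58.

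| Bias, in SD of one reading | One time point, α = 0.05 | Mean of five, α = 0.05 |
|---|---|---|
| 0.10 | 6% | 10% |
| 0.25 | 12% | 39% |
| 0.50 | 32% | 92% |

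The same assumed bias thus gives very different rates depending on how the readings are combined. The documents give no SD, so none of these values can be expressed in mm.

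**The case against.** The strongest reply is that this is a disclosed design choice. The plan calls itself single-blind, says who is blinded, and contradicts itself nowhere on this point. That is correct: there is no inconsistency, and no figure in the plan would change. But disclosing a weakness does not remove it, and here it can be reduced cheaply.

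The second reply is that safeguards already exist: a blinded participant, a 0.1 W placebo laser with otherwise identical settings, an endpoint triggered by the participant, and the same two people at every site within each participant. These narrow the exposure. They do not cover handling and reading by someone who may know the allocation.

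The third reply is that the numbers say little about this trial, because everything beyond n and α is assumed. That stands. The tables show how a bias would act, not how large it is.

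A reader might infer from section 5.1 that the operator knows the mode at every site. The documents do not establish this. Two modes are predefined and the order is random, so presetting parameters does not by itself reveal which mode is used where. Nor does the plan leave the tester wholly unidentified: section 2 confines the task to the operator and assistant, and only the split between them is open.

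**Conclusion.** The gap is real. Followed as written, the plan allows penetration depth to be measured by someone who knows the site's allocation, and it includes no standard handling that would limit the consequences. This should be corrected, but it does not invalidate the design.

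The size and direction of any bias cannot be derived from the documents. The false-positive rates rest wholly on an assumed bias, a simplified test and an assumed number of comparisons. Biases well below about 0.15 to 0.18 SD of the paired difference would have little effect on the error rate, and larger ones would matter. Bonferroni correction lowers the rates but does not remove a systematic difference. It would go too far to read this as evidence that depth will be biased, or biased in favour of the laser.

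Confidence is medium, because the point depends on what a short protocol leaves unsaid.

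**What to change.** Amend sections 2, 3.1.3, 5.1 and 5.2 to assign each task to one of the two people already present.

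- **Treating person:** holds the allocation, presets and selects the predefined mode, irradiates, and applies the gel or jelly.
- **Tester:** performs all penetration tests and records depth, VAS and heart rate by site code only. The tester stays out of sight of treatment. If needed at irradiation, the tester works with the mode display hidden and is away for the application.
- **Measurement:** one standard needle advance and one standard way of reading the exposed length, written down and used at every site. This part helps even if masking is imperfect.

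As written, the operator both presets the laser and records VAS, so section 5.1 or section 3.1.3 must change to keep these tasks apart. Section 2 would then say that participants and the penetration tester are blinded to group assignment. If the roles cannot be split, the protocol and the report should state that depth was assessed unmasked.

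The cost is protocol wording and some choreography. No extra staff are needed if both people are qualified for their tasks, which the documents do not state; nor do they say how treatment of the three sites is spaced in time. Masking may be incomplete: visible tissue effects or jelly residue could reveal a site, and so could earlier responses, since 240 of the 300 tests follow an earlier test at the same site.

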3.1 Experimental Equipment

3.1.1 Water Laser Device

Device: Er,Cr:YSGG Waterlase (Model MDX300), manufacturer: BOOLASE (USA), registration number: National Medical Device Approval 20153241177. The laser wavelength is 2780 nm and is suitable for various dental procedures. Two modes are predefined:

- Mode 1a (active laser): Power 1.0 W, water 15%, air 35%, frequency 30 Hz, H mode (soft tissue mode);
- Mode 1b (placebo laser): Power 0.1 W, other parameters same as Mode 1a.

All personnel must wear laser protective glasses during operation. The handpiece must be moved continuously to avoid localized heat accumulation.

3.1.2 Electrocardiogram (ECG) Monitor

Device: Baolaite M7000 Multi-parameter Monitor (Guangdong Medical Device Approval 2012 No. 2210328), used for continuous monitoring of heart rate, blood pressure, and oxygen saturation. The cuff is placed on the upper arm, and the oxygen sensor is attached to the index finger. Data will be recorded throughout the procedure.

3.1.3 Visual Analog Scale (VAS)

A 10 cm linear VAS will be used to assess pain intensity, ranging from "no pain" (0) to "worst pain imaginable" (10). Participants will slide the indicator to reflect their subjective pain level, and the operator will record the corresponding value.

3.2 Experimental Drugs and Materials

- Topical anesthetic: 2% lidocaine gel (Gandermal, Registration No.: H20150426);
- Placebo: Petroleum jelly;
- Other materials: 27G injection needle (Fukada), periodontal probe (Hu-Friedy), mouth prop (Ivoclar), dental mirror, sterile cotton swabs, timer, etc.

4. Outcome Measures

Primary outcome measures include:

- Penetration depth and VAS score at the moment of "sensation of foreign body";
- Penetration depth and VAS score at the moment of "pain";
- Heart rate at each needle insertion and the increase in heart rate (heart rate at pain moment – baseline heart rate).
- Penetration depth is calculated based on the exposed length of the needle (penetration depth = 30 mm – length outside the mucosa).

5. Study Procedure

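### Six unranked primary outcomes, no primary contrast and an undefined Bonferroni family leave the false-positive rate for the laser claim uncontrolled

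*Combined protocol and SAP*

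**What the plan says.** Section 4 (Outcome Measures) begins "Primary outcome measures include" and gives depth and VAS at two moments, which makes four measures, followed by "Heart rate at each needle insertion and the increase in heart rate", which makes six. The last bullet only defines how depth is calculated. No measure is ranked above another.

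Section 5.2 sets the repetition: "Penetration tests will be performed at 10, 20, 30, 40, and 50 minutes after treatment". It adds that "Penetration depth, VAS score, and heart rate will be recorded at the moments of" sensation and pain.

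Section 6 states the analysis in three relevant sentences: "Repeated measures ANOVA will be used to compare differences across time points and groups"; "Pairwise comparisons will be performed using Bonferroni correction with significance level" 0.05; and "A p-value < 0.05 will be considered statistically significant".

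Section 2 defines three interventions. Experimental and Control both receive lidocaine gel and differ in laser power (1.0 W against 0.1 W). The third is "Blank group: Irradiation with placebo laser (0.1 W) for 1 minute, followed by application of petroleum jelly". Neither section 4 nor section 6 names a primary contrast, a primary time point or a rule for declaring the trial successful.

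**The concern.** The title asks whether the laser improves topical anaesthesia, and only Experimental versus Control answers that. The plan allows this contrast to be read from any of six outcomes and, on one reading, from any of thirty outcome-by-time comparisons, with nothing to prevent the best of them being presented as the primary result.

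The Bonferroni sentence does not close the gap. With three interventions it corrects over three pairs within one outcome and does nothing across outcomes. It also leaves open whether its family is three pairs or fifteen pair-by-time comparisons, a choice that could be made after seeing the data.

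Nor does the three-group test help. Blank receives no lidocaine, so if lidocaine works, a significant three-group result is a true positive that says nothing about the laser.

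**Working it through.** The documents state no family-wise error or power figure, so there is none to reproduce.

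**Inputs from the documents.** Six primary measures (section 4); three interventions, hence three pairs (section 2); five test times (section 5.2); α = 0.05 with Bonferroni on pairs (section 6); 20 participants with three sites each (sections 1 and 2).

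**Assumptions.** Two-sided tests; a common correlation ρ of 0.3, 0.5, 0.7 or 0.9 between test statistics, since the documents give none; no true laser effect.

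**Formulas.** For k tests at level a: independent, 1 − (1 − a)^k; upper bound under any dependence, k × a. Correlated values come from numerical integration of an equicorrelated normal.

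**Chance of at least one significant Experimental-versus-Control primary**

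| Reading | k | a | Independent | Bound | ρ = 0.3 / 0.5 / 0.7 / 0.9 |
|---|---|---|---|---|---|
| Time-averaged, three-pair Bonferroni | 6 | 0.05/3 | 1 − 0.98333^6 = 9.6% | 10% | 8.9 / 7.8 / 6.2 / 4.0% |
| Each time, three-pair Bonferroni | 30 | 0.05/3 | 1 − 0.98333^30 = 39.6% | 50% | 31 / 23 / 15 / 7% |
| Each time, Bonferroni over fifteen | 30 | 0.05/15 | 1 − 0.99667^30 = 9.5% | 10% | 8.1 / 6.2 / 4.0 / 1.7% |

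**The count of six.** Section 5.1 describes one baseline heart rate. If heart rate is analysed at the pain moment, subtracting one value per participant leaves the difference between that participant's sites unchanged, so heart rate and its increase are the same group test. Five distinct tests give 8.1% time-averaged (7.6 / 6.8 / 5.6 / 3.7% at the same ρ). Testing them at each time (25 tests at 0.05/3) gives 34% if independent (28 / 21 / 14 / 7%). If heart rate is analysed at both moments there are seven variables, six of them distinct with a single baseline; seven independent tests would give 11.1%.

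**Small-sample check.** In 40,000 simulated trials of 20 participants with thirty paired t tests at 0.05/3, the rate was 39.4 / 32.6 / 24.5 / 16.0 / 7.4% at ρ = 0 / 0.3 / 0.5 / 0.7 / 0.9. With separate outcome and time correlations, both set to 0.3 and then both to 0.9, it was about 36% and 9%.

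**Does the three-group F test protect?** With Experimental equal to Control and Blank lower by an assumed 1 SD, requiring a significant F test first left the six-outcome rate at 9.6% if independent and unchanged at each ρ. With all three groups equal, it fell from 9.6% to 7.6%.

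**Power, Experimental versus Control.** Noncentral t, n = 20 paired, with assumed differences in units of the SD of the paired difference:

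| Level | 0.5 | 0.65 | 0.8 | 1.0 |
|---|---|---|---|---|
| 0.05 | 0.565 | 0.787 | 0.924 | 0.989 |
| 0.05/3 | 0.373 | 0.615 | 0.818 | 0.958 |
| 0.05/6 | 0.273 | 0.501 | 0.729 | 0.921 |
| 0.05/18 | 0.156 | 0.337 | 0.567 | 0.828 |

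**The case against.** The best reply is that 40% is an extreme. It needs thirty independent tests, yet depth and VAS at both moments come from the same needle insertion and the five times are repeated on the same sites. It also needs two readings the plan does not state: judging the laser at each time, and correcting over three pairs only. With Bonferroni over all fifteen comparisons the rate is at most 10%. On the time-averaged reading, inflation is modest and may be absent: six tests give 5.2% at ρ = 0.8 and 4.0% at 0.9, and five distinct tests give 4.7% at 0.8. It can also be said that the arm labels make the intended contrast evident.

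Much of this stands as a limit on the size. The 40% is conditional, the correlated ranges depend on the model, and error above 5% is not certain on every reading. It does not remove the defect. The document permits a laser-specific error from under 5% to about 40%, depending on choices it does not make, and even the favourable readings leave unstated which result counts as success. An evident contrast is still not a designated one.

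**Conclusion.** The concern holds and should be fixed before the analysis. Sections 4 and 6 do not fix the false-positive rate for the question in the title. It is 9.6% if outcomes are independent and each has one time-averaged test at 0.05/3, and 4.0% to 8.9% at correlations of 0.9 to 0.3. Testing at each time with three-pair correction raises it to 40% if independent (7% to 31% correlated). The independent figures follow from the plan's own counts and α. The correlated ones rest on assumed values, and the thirty-test range shifts to about 9% to 36% under a separate outcome-by-time structure. The absence of a success rule, an outcome hierarchy and a primary contrast depends on none of these assumptions.

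**What to change.** In sections 4 and 6, before outcome data are examined, name one primary outcome, one summary over time and one contrast. An example is Experimental versus Control in penetration depth at the 'pain' moment, averaged over the 10 to 50 minute tests, two-sided 0.05. If an effect confined to some times is expected, choose a different summary, but fix it in advance. Then:

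- Make the other outcomes secondary, with Holm across the five remaining Experimental-versus-Control tests (four if heart rate and its increase are the same test).
- Report Control versus Blank, whatever the laser result, as a check that the method detects lidocaine; keep it outside the primary claim.
- Treat per-time comparisons as supportive.

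If all six stay primary, choose one of two rules:

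- **All must succeed.** No adjustment across outcomes is then needed. With the same effect on each and ρ = 0.5, power is 0.18 / 0.44 / 0.73 / 0.95 at standardised differences of 0.5 / 0.65 / 0.8 / 1.0 (0.03 / 0.24 / 0.62 / 0.93 at ρ = 0; 0.39 / 0.65 / 0.85 / 0.97 at ρ = 0.9).
- **Holm or Bonferroni across the six.** For Bonferroni the level is 0.05/6 = 0.0083 with one contrast, or 0.05/18 = 0.0028 if the three-pair correction is kept. Against a single test at 0.05, the power loss is 29 / 29 / 20 / 7 points or 41 / 45 / 36 / 16 points respectively.

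The cost is wording, with no new data. One named test at 0.05 has more power than the three-pair Bonferroni (0.787 against 0.615 at a standardised difference of 0.65). The price is that an isolated VAS or heart-rate result could no longer be called primary success. The documents do not give recruitment status; choosing the outcome after seeing results would not remove the selection.
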